Our study group has extensive experience with the inpatient Rehabilitation brain injured population, research experience in regards to sleep after brain injury, and demonstrated use of light therapy and actigraphy in individuals with TBI ([name] DJ, 2012) (Watson NF, 2007). The University of Washington investigators have current IRB permission to conduct a pilot study of BWL exposure on the acute rehabilitation unit to allow for the current study protocol to be refined early in the research process and demonstrate logistics and feasibility to collaborating TBIMS centers. In the current health care climate, low cost treatments with low staff burden are valued and we will evaluate these factors in this study (Wood RL, 1999) (Whitmore RG, 2012).

II. Target Population:

Individuals aged 18-70 years with moderate to severe traumatic brain injury (TBI), 30 days or less out from TBI hospitalized on acute inpatient rehabilitation. Moderate to severe TBI will be determined using the TBI Model System (TBIMS) case definition (Traumatic Brain Injury Model Systems, 2013): damage to brain tissue caused by an external mechanical force, post-traumatic amnesia (PTA) greater than 24 hours, or loss of consciousness greater than 30 minutes or Glasgow Coma Scale (GCS) score in the Emergency Department of 3-12, or intracranial abnormalities on imaging (Cuthbert JP, 2012).

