The screening process will begin will reviewing the medical charts for patients that are on the inpatient rehabilitation unit at Harborview Medical Center. If a patient meets the inclusion criteria, research staff will approach the patient to determine whether the patient is cognitively capable of giving their consent for the study by administering the Galveston Orientation and Amnesia Test. The study will then be explained to the patient; or if the patient is experiencing post traumatic amnesia, the study will be explained to the patient’s legally authorized representative. Consent will be obtained either from the patient or, if he or she is unable to provide informed consent, the patient’s legally authorized representative.

VII. Study Sample:

Study participants will be recruited from acute inpatient rehabilitation at three participating TBI Model Systems institutions (University of Washington, Mount Sinai, Baylor). Eligible participants will be within three months of sustaining a moderate to severe TBI (as defined by the TBI Model Systems (Traumatic Brain Injury Model Systems, 2013)), admitted to acute inpatient rehabilitation, English speaking, and aged 18-70 years. Exclusionary medical factors will be identified in the medical record and through interview during screening/baseline assessment. In a pilot study comparing the effects of BWL and RL exposure in a sample of subjects with chronic TBI, Cantor et al. (Cantor, et al., 2012) reported an effect size of 0.63 for sleep duration. Because this pilot study involved subjects in the chronic phase of TBI, who were living at home rather than in an institution, and underwent a longer course of treatment (28 days in that study vs. 10 days in this study), we chose to take a conservative approach to calculating the required sample size. Based on an estimated effect size of 0.5 and 80% power, 128 subjects would be required to complete this study (64 per group). We anticipate recruitment over three years at three sites. Historical TBIMS and associated trial enrollment totals from the participating sites supports this study enrollment goal.

VIII. Inclusion Criteria:

1. Within three months of moderate to severe TBI
2. Admitted to acute inpatient rehabilitation
3. Ages 18-70
4. English speaking

VIII. Exclusion Criteria:

1. Complete blindness
2. Absence of eye opening or disorders of consciousness (Rancho level of 1-3)
3. Past medical history of retinal pathology
4. Past medical history of light sensitivity

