Medical History	Diagnoses, medications at enrollment, symptoms, associated injuries (ICD-9 codes), vital signs	X		
Berlin questionnaire	Sleep apnea	X		
Clinician Rating: Delirium Rating Scale Revised 98 Item 1	Sleep disturbance	X		
Makley scale	Sleep disturbance	X	X	
Actigraphy	Sleep parameters	X	X	
Light Therapy Time	Light exposure time		X	
Medication categories	Potential confounders (see data sheet)	X		X
FIM™ Scores and Efficiency	Functional score	X		X
Hospitalization	Acute LOS, Rehab LOS	X		X
Symbol Digit Modalities Test	Attention	X		X
PANAS	Mood	X		X
Therapy participation	Function	X		X
Karolinska Sleepiness Scale	Daytime sleepiness	X		X
Barrow Neurological Institute Fatigue Scale	Daytime fatigue	X		X

A. Screening Measures:

The following data will be used as descriptive characteristics of the subjects upon study completion. Initially this data will be used during the screening process to ensure appropriate patients are approached for participation:

- **Demographics:** Age, gender, race/ethnicity, weight (kg), height (cm), BMI (calculated).

- **Injury Characteristics:** Time since injury, Post-resuscitation GCS score, duration of PTA as measured by TBIMS procedures using the Galveston Orientation and Amnesia Test (GOAT), associated injuries including ICD codes.
- **Medical History:** Current diagnoses, past diagnoses, medications (at enrollment, during treatment and at outcome measure), vital signs.
- **Berlin Questionnaire** (Netzer NC, 1999): The 10-item questionnaire consists of 3 categories related to the risk of having sleep apnea. Patients can be classified into High Risk or Low Risk based on their responses to the individual items and their overall scores in the symptom categories.

B. Randomization Measure:

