- 3) Clinical Staff feedback: phototherapy intervention will rated using a likert scale on the following categories:

- a. Ease of use
- b. Perceived relevance to rehabilitation care
- c. Impression of effectiveness.

Post Light Therapy Outcome Assessment

Day 13: At the conclusion of the light therapy sessions (and prior to discharge from rehabilitation), a blinded Outcomes Examiner will complete the post therapy outcome assessment. This assessment will include the following:

- Symbol Digit Modalities Test
- Positive and Negative Affect Schedule (PANAS)
- Barrow Neurological Fatigue Scale

XII. Data Analysis

The primary outcome is the between-group difference (BWL vs. RL exposure) in average sleep efficiency at baseline compared to after 10 days of light treatment. ANOVA will be used to compare groups controlling for demographics, injury severity, and use of medications.

Secondary outcomes (mood, therapy participation, attention, daytime sleepiness/fatigue) between groups assessed at baseline and after 10 days of light therapy will be compared using repeated measures ANOVA. FIMTM efficiency and inpatient rehabilitation length of stay will also be compared between groups using ANOVA controlling for the same variables as the primary outcome. Descriptive analysis will summarize responses to the nursing burden questions including estimated staff time for the intervention.

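### The stated covariates leave out the randomisation strata, the baseline value and time since injury, all of which are already collected; precision is lost but no bias arises

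*Combined protocol and SAP*

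**What the plan says.** - **Primary model (section XII, Data Analysis).** "ANOVA will be used to compare groups controlling for demographics, injury severity, and use of medications". The contrast is between groups, at baseline and after 10 days of light.
- **FIM efficiency and length of stay (same section).** "ANOVA controlling for the same variables as the primary outcome".
- **Mood, participation, attention, sleepiness and fatigue (same section).** These "will be compared using repeated measures ANOVA", and no covariates are stated.
- **Randomisation (section XI, Baseline and Randomization).** Stratified by centre (three sites) and by severity on DelRS-R98 item 1 (mild, moderate, severe). Neither factor appears in section XII.
- **Time since injury (section X.A, Screening Measures).** Collected as an injury characteristic: "Time since injury, Post-resuscitation GCS score, duration of PTA as measured by TBIMS procedures". The stated use of this block, besides screening, is descriptive: "The following data will be used as descriptive characteristics of the subjects upon study completion".
- **Entry window.** Section VII (Study Sample) says "Eligible participants will be within three months of sustaining a moderate to severe TBI", and the inclusion criteria and the appendix checklist agree. Section II (Target Population) says "30 days or less out from TBI hospitalized on acute inpatient rehabilitation".

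**The concern.** Three kinds of baseline information are in hand but not in the stated models.

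1. **Strata.** Stratifying balances centre and sleep severity between arms. If these factors predict sleep efficiency and the analysis ignores them, their variance stays in the error term and the standard error is larger than the design warrants.
2. **Baseline value.** Baseline sleep efficiency is measured and enters the comparison, but it is not named as a covariate. A change-type comparison generally uses it less efficiently than ANCOVA does.
3. **Time since injury.** Under the operative criteria it can range up to three months. If recovery stage is related to the outcomes, leaving it out keeps that variance in the error term and leaves any chance imbalance in the estimate.

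What is at stake is precision and protection against chance imbalance. Terms added after unblinding would be post hoc, so they need to be fixed beforehand.

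**Working it through.** **Inputs.** From section VII: standardised effect 0.5, power 80%, 128 completers, 64 per group. Alpha is not stated; two-sided 0.05 is assumed.

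**Reproducing the plan's figure.** A two-sample t-test with d = 0.5, 80% power and two-sided 0.05 needs 63.77 per arm, so 64 per arm and 128 in total. This matches. A one-sided 0.05 test would need about 100 in total and does not match. Power at 64 per arm is 80.1%.

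**Time since injury: gain from adjusting.** Let r be its partial correlation with the outcome after the other covariates. The documents give no value, so r is an assumption. Adjustment multiplies the residual SD by √(1 − r²), so the effect becomes 0.5/√(1 − r²).

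**Time since injury: exposure without adjusting.** The 95% range for chance imbalance between arms is 1.96 × √(2/64) = 0.346 SD of the covariate. Left unadjusted, it moves the estimate by up to r × 0.346 outcome SDs.

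| Assumed r | Effect after adjustment | Power, 64 per arm | Total N for 80% | 95% shift if unadjusted (SD) |
|---|---|---|---|---|
| 0 | 0.500 | 80.1% | 128 | 0 |
| 0.1 | 0.503 | 80.5% | 128 | 0.035 |
| 0.2 | 0.510 | 81.7% | 124 | 0.069 |
| 0.3 | 0.524 | 83.7% | 118 | 0.104 |
| 0.4 | 0.546 | 86.5% | 108 | 0.139 |

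The shift compares with a planned effect of 0.5 SD. It is random in direction and averages zero over randomisations.

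**Baseline value.** With equal variance σ² at both times and baseline-to-outcome correlation ρ, the variance per patient is 2σ²(1 − ρ) for a change score and σ²(1 − ρ²) for ANCOVA. The ratio is (1 + ρ)/2, which is never above 1. The documents give no ρ; for an assumed 0.3 to 0.7 the ratio is 0.65 to 0.85.

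**Cost in degrees of freedom.** Baseline 1, centre 3 − 1 = 2, severity 3 − 1 = 2, time since injury 1: six in total. The checklist admits a DelRS-R98 rating of 0 if sleep medication was taken in the last 72 hours. If such patients form their own stratum, the total is seven. Moving from 126 to 120 residual degrees of freedom at d = 0.5 leaves power at 80.1%.

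**If the added terms predict nothing.** Expected variance inflation from q such covariates is about 1 + q/(128 − 2 − q − 1).
- For time since injury alone: 1 + 1/124 = 1.008, power 79.8%.
- For all six, as an upper bound: 1 + 6/119 = 1.050, power 78.2%. The strata are balanced by design, so their share is smaller than this formula allows.

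**The case against.** The strongest reply is that no error has been shown. The trial is randomised, so omitting a baseline covariate biases nothing, and which covariates to include is a design choice. That stands, and it limits the point to efficiency.

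Several other replies also stand in whole or in part:

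- **Section II does not call time since injury prognostic.** A reader might infer it, because the section says limits on age and on time since injury are needed. But the physiological reason given there belongs to age; the reason for time since injury is that the study targets early recovery, which is a matter of scope.
- **No relation is documented.** Nothing in the documents links days since injury to sleep efficiency, attention, fatigue or FIM gain within the enrolled window. A worthwhile gain in power cannot be claimed, and r may be close to zero.
- **The design absorbs part of it.** Comparisons with baseline and repeated measures remove stable level differences, so only differences in change over about 10 days remain. Stratifying on sleep severity may balance a correlate too. This does not apply to FIM efficiency or length of stay in the same way.
- **The spread is uncertain.** With a 30-day window time since injury varies less than with three months.
- **The list names categories, not variables.** It is therefore too strong to call it closed. Still, time since injury does not fit naturally under any heading: section X.A lists it as an item separate from GCS and PTA duration, and it is not among the demographics there. Centre and the baseline outcome value fit none of them either.

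What survives is that measured information, including the factors used to randomise, has no stated place in the models.

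**Conclusion.** The point holds as a low-cost improvement to the analysis. The primary, FIM efficiency and length-of-stay models name only demographics, injury severity and medication use, and the repeated-measures models name no covariates. The strata and the baseline value are the main omissions; time since injury is a secondary one.

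For time since injury, power at 64 per arm and d = 0.5 lies between about 80% and 86.5% if the partial r is 0 to 0.4. That range is assumed, and its lower end is no gain at all. Without adjustment, chance imbalance could move the estimate by up to about 0.14 SD at r = 0.4. These figures also assume two-sided alpha 0.05, which reproduces the planned 128.

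A reader might infer that the omission biases the treatment comparison or leaves the trial underpowered. The documents support neither: allocation is randomised, and the planned sample size reproduces without these covariates.

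**What to change.** In section XII, prespecify:

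- **Primary:** ANCOVA of post-treatment sleep efficiency on treatment, baseline sleep efficiency, centre, sleep-severity stratum and days from injury to randomisation (continuous), in addition to the demographic, injury-severity and medication terms already listed, each named at variable level.
- **Repeated-measures secondary outcomes:** the matching baseline value, the strata and time since injury.
- **FIM efficiency and length of stay:** the strata and time since injury, with admission FIM where applicable.
- **Severity stratum:** state how patients admitted with a rating of 0 are classified.
- **Entry window:** reconcile section II with section VII, the inclusion criteria and the checklist, since the spread of time since injury depends on it.

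The cost is about six degrees of freedom out of roughly 128 patients and no new data. The change should be made before unblinding.

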Aim 1: In persons with TBI, prospectively compare overnight sleep efficiency in a cohort exposed to morning Bright White Light with a comparison group exposed to Red Light in an acute inpatient rehabilitation setting.

Aim 2: Explore the relationship between Bright White Light exposure during inpatient rehabilitation after TBI and mood, therapy participation, attention, rate of functional recovery and length of stay.

Aim 3: Develop and describe sleep study procedures on the inpatient rehabilitation unit for persons with TBI to support optimal and feasible design of future studies in this important area.

Research Hypothesis:

In persons with TBI, prospectively compare overnight sleep in a cohort exposed to morning Bright White Light with a comparison group exposed to Red Light in an acute inpatient rehabilitation setting.

Hypothesis 1: Individuals exposed to Bright White Light for 30 minutes each morning will have better sleep compared to the Red Light exposure group, as measured by sleep efficiency.

Hypothesis 2: Individuals with daily morning Bright White Light exposure will have better mood (as measured by the Positive and Negative Affective Schedule, PANAS), therapy participation (as measured by a 0-100 therapist rating) and attention (as measured by the Symbol Digit Modalities Test) at 10 days compared to individuals with daily Red Light exposure. The group exposed to Bright White Light will also have less daytime sleepiness and fatigue (as measured by the Karolinska Sleepiness Scale (KSS) and the Barrow Neurological Institute Fatigue Scale (BNI-FS), a faster rate of functional recovery as measured by FIM™ efficiency for the rehabilitation stay and a shorter length of stay compared to those in the Red Light group

Hypothesis 3a: Bright White Light exposure will be rated as a reasonable addition to clinical care by staff using Likert scale ratings. Categorize and quantify rates of any side effects of Bright White Light and Red Light exposure in persons with TBI during inpatient rehabilitation.

Hypothesis 3b: Bright White Light and Red Light exposure will be generally well tolerated with side effect profiles and rates similar to those observed in previous studies with other populations.

[figure not shown]
See Appendix for Flowchart on Specific Aims of this study

V. Study Description

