Day 0-1 (2 days): After determining eligibility, the participant will be fitted with an Actiwatch (actigraphy) for continuous monitoring of activity levels both during the day and night (American Sleep Disorders Association, 1995). The Actiwatch will be worn continuously (with removal as needed for hygiene, shower or other clinical care) from enrollment to outcome measurement. Actiwatches will be fully charged and cleared of all previous data before being provided to a subject. Units will be set to record activity data in 60-second epochs. Actiwatches have sufficient built-in memory capacity and battery life to be used for approximately 30 days without recharging. Additionally, sleep logs that rate patient sleep are filled out every hour, between the hours of 2200-0600, this information is then obtained

as completion of the Makley scale. A complete review of symptoms and medical history will be obtained from the subject, LAR, and medical records.

Day 2: Baseline data collection is obtained (See Appendix for Baseline Data Collection Forms). Measures collected include: Symbol Digit Modalities Test, Positive and Negative Affect Schedule (PANAS), Barrow Neurological Fatigue Scale. Clinical Staff, will be asked if there was sleep difficulties and therapist will be asked to rate therapy participation for that day.

Day 2: Randomization. After baseline testing is completed, subjects will be randomized (50:50) using a 2-level stratification design based on two pieces of information:

- 1) Center (U. Washington-Seattle, Baylor-Dallas, Mount Sinai-New York) and
- 2) Severity of Sleep Disturbance using Delirium Rating Scale-Revised 98 Item 1

The rating for the Delirium Rating Scale Item 1 are: 1=Mild, 2=Moderate, 3=Severe

(Nakase-Richardson R S. M., Prospective evaluation of the nature, course, and impact of acute sleep abnormality following TBI , 2013) Using an Access Database, developed by [name] at the University of Washington, centers will randomize the participant into either the Bright White Light Group or the Dim Red Light Group. [46]

Light Therapy:

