Days 3-13: Each morning for 10 days, the research and/or nursing staff will set up the Litebook® device in the marked out area of the bedside table. The light will be between 12 and 24 inches from the subject, allowing light to reach the subject's eyes. The subject will be in front of the device for 30 minutes, eating or otherwise doing relaxing activities and will have the eyes open. Both BWL and RL will be delivered using a Litebook® (The Litebook Company Ltd; Medicine Hat, Alberta, Canada). The Litebook® is a small (6 inch x 5 inch x 1 inch) unit with an attached stand that is placed 12-24 inches from the user's face and within 45 degrees of the visual field per manufacture guidance. Both the BWL and RL devices contain a data log to track the times at which the light box is turned off and on allowing the total time of exposure to be calculated. The cases for the BWL and RL units are visually identical. Research Staff will setup the Litebook ® on the bedside/over bed table as part of the subjects' morning/breakfast daily routine. The research staff will check in with nursing staff and the patient/LAR regarding adverse effects each day. Study medical staff will also be available for study questions or problems at other times and the patient's primary medical service will also be following for their overall medical care per routine. Nursing staff will be trained regarding the light exposure protocol as part of preparation for the study and the individualized setup for each subject will be reviewed and diagrammed in their room on enrollment. Subjects will receive 10 morning sessions of their assigned light therapy (BWL vs. RL).

Additional Data Collected

- 1) Sleep Logs: Sleep logs will be integrated with overnight nursing rounds. Trained nursing staff will perform regular ratings every hour of sleep/wakefulness between 2200-0600 using the Makley Scale, a 4-point ordinal scale ranging from 0 (asleep) to 3 (awake). This paper sleep log will be collected daily by the research study staff. This is part of routine rehabilitation care and will not add any sleep disruption for study participants. Sleep logs will be used as one tool to help interpret overall actigraphy data patterns during analysis.
- 2) Therapy Participation: The physical therapist will be asked by the research staff to rate at both baseline days and on the final two days outcome assessment time points.

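### The repeated measures ANOVA for the secondary outcomes names no deciding term, and its likely intended group-by-time test is less precise than a baseline-adjusted Day 13 comparison

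*Combined protocol and SAP*

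**What the plan says.** Section XII gives the five outcomes (mood, therapy participation, attention, sleepiness, fatigue) one sentence: they "between groups assessed at baseline and after 10 days of light therapy will be compared using repeated measures ANOVA". No model, term or contrast is named there or elsewhere.

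Hypothesis 2 (Section IV) predicts better mood, participation and attention "at 10 days compared to individuals with daily Red Light exposure". It then predicts less sleepiness and fatigue without repeating the time point.

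Table 1 (Section X) schedules all five at baseline and on Day 13. Section XI places baseline before allocation: "After baseline testing is completed, subjects will be randomized (50:50) using a 2-level stratification design". Light starts on Day 3.

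Therapy participation is less clear. Section X.D has it rated at enrollment and on Day 13. Section XI (Additional Data Collected) has the physical therapist "rate at both baseline days and on the final two days outcome assessment time points".

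FIM efficiency and length of stay are also in Hypothesis 2, but Section XII assigns them an ordinary ANOVA with covariates. They are outside this point.

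**The concern.** With two arms and two time points, a repeated measures ANOVA returns two tests that involve arm.

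- **Group-by-time interaction.** This compares the arms on change from baseline. It targets the right quantity, but it subtracts the whole baseline score whatever the correlation between the two measurements. The noise in the baseline therefore enters the contrast.
- **Group main effect.** This compares the arms on the average of baseline and Day 13. Light cannot have affected the baseline half.

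Hypothesis 2 asks for a difference after 10 days, and the plan does not tie that to either line. At stake are the precision of every comparison under this method, and a choice of test that remains open when the data are analysed.

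**Working it through.** **Inputs.** From Section VII: effect size 0.5, power 80%, 64 per group. That calculation is for sleep; none is given for these outcomes. Alpha is not stated. The baseline-to-Day-13 correlation ρ is not given either. The only related figures are the PANAS 8-week retest correlations in Section X.D, .39 to .71. I assume ρ from 0.3 to 0.71, equal SDs of 1 at both times, complete pairs, and a true Day 13 effect d = 0.5.

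**Step 1: reproduce the plan's sample size.** Two-sided 5% with a normal approximation gives 2 × (1.960 + 0.842)² / 0.5² = 62.8, so 63 per group. By the t test, 64 per group has power 80.1% and 63 has 79.5%. One-sided 5% gives 50 per group and does not reproduce the plan. Two-sided 5% is therefore used below.

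**Step 2: standardised effect of each contrast.** The expected baseline difference is zero by randomisation.

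- Group main effect: (0 + d)/2 = 0.25, with SD √((1+ρ)/2)
- Group-by-time (change score): d, with SD √(2(1−ρ))
- Day 13 alone: d, with SD 1
- Day 13 adjusted for baseline (ANCOVA): d, with SD √(1−ρ²)

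At ρ = 0.5 these give 0.25/0.866 = 0.289, 0.5/1 = 0.500, 0.500, and 0.5/0.866 = 0.577.

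**Step 3: power, 64 per arm, noncentral t, two-sided 5%.**

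| ρ | Main effect | Group-by-time | Day 13 alone | ANCOVA |
|---|---|---|---|---|
| 0.30 | 41% | 66% | 80% | 84% |
| 0.39 | 39% | 72% | 80% | 86% |
| 0.50 | 37% | 80% | 80% | 90% |
| 0.71 | 33% | 96% | 80% | 98% |

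Simulation of 20,000 trials at each of ρ = 0.39, 0.5, 0.6 and 0.71 agreed for the first three contrasts. The main-effect estimate averaged 0.25, confirming the halving. The ANCOVA column is from the formula.

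**Step 4: precision of the two serious candidates.** The variance ratio, group-by-time to ANCOVA, is 2(1−ρ)/(1−ρ²) = 2/(1+ρ). This is 1.54 at ρ = 0.3, 1.33 at 0.5 and 1.17 at 0.71. It exceeds 1 whenever ρ is below 1. In patients, 64 × 1.33 = 85: at ρ = 0.5 the change-score test would need about 85 per arm to match ANCOVA with 64.

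**The case against.** The strongest reply is that nobody would use the main effect. That largely stands. A reader might take the words about comparing between groups as the ANOVA-table label for the main effect, and conclude that the plan has chosen a test with about 37% power. The documents do not support this. The phrase is ordinary English for comparing the arms. The preceding paragraph of Section XII ties the primary outcome's between-group difference to baseline compared with post-treatment, which suggests change by arm. Nothing proposes averaging over the two times, and Hypothesis 2 points away from it.

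Two other strong readings also fail.

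- **Inflated false positives.** Accepting either ANOVA line if significant would give about 9.7% per outcome in simulation, but nothing suggests the investigators would choose that way.
- **Opposite conclusions.** With a true effect, the main effect and the interaction give different verdicts in 52% to 65% of simulated trials. That means significant versus not significant, not a reversed direction, and one of the two is the unlikely candidate.

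It is also fair that Aim 2 is worded as exploration, that the trial is sized for sleep, and that naming group-by-time would remove the ambiguity within the stated method. Against that, Hypothesis 2 makes directional predictions for each measure, and group-by-time would leave precision unused. At ρ = 0.3 it is weaker than ignoring baseline altogether (66% against 80%).

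**Conclusion.** The point holds as a low-cost improvement with a needed clarification; it does not show that the plan has specified a wrong test. Section XII leaves the deciding term unnamed. On the charitable group-by-time reading, the contrast has 1.54, 1.33 and 1.17 times the ANCOVA variance at correlations 0.3, 0.5 and 0.71, with power lower by 18, 10 and 2 percentage points. On the unlikely main-effect reading, the expected effect is halved and power is 33% to 41%.

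The power figures rest on assumptions: 64 complete pairs per arm, 0.5 SD, two-sided 5%, equal variances, and correlations the plan does not supply. They illustrate size and do not show a missed target. The halving and the variance ratio do not depend on the effect size. Missing baseline scores would change the numbers.

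**What to change.** Replace the repeated measures ANOVA sentence in Section XII with:

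> For each secondary outcome measured at baseline and Day 13, the deciding contrast is the BWL minus RL difference in the Day 13 score, estimated by ANCOVA with the baseline score of that measure as covariate; the group effect averaged over baseline and Day 13 will not be used.

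Two additions make it workable.

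- **Therapy participation.** Reconcile Sections X.D and XI on the number of ratings. If two are taken at each end, use the mean of the baseline ratings and the mean of the final ratings.
- **Missing baseline scores.** The baseline sleepiness and fatigue forms in the Appendix have a box for patients who cannot report, and patients still in post-traumatic amnesia may enrol by proxy consent. Keep such patients in the analysis, for example by a mixed model for baseline and Day 13 with the baseline means constrained equal across arms. It targets the same Day 13 contrast.

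The cost is a few sentences of text. The data are already scheduled; no extra patients, visits or staff time are needed.
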